15.3 Audits and Inspections

The Investigator should understand that source documents for this study should be made available to appropriately qualified personnel from the Sponsor or its designees, or to health authority inspectors after appropriate notification. The verification of the CRF data must be by direct inspection of source documents.

15.4 Case Report Forms

The data collected in the source documents for this study will be entered into the study EDC CRF. An audit trail will maintain a record of initial entries and changes made; time and date of entry; and name of person making entry or change. For each participant enrolled, a CRF must be completed and signed by the Principal Investigator or authorized delegate from the study staff. If a participant withdraws from the study, the reason must be noted in the CRF. If a participant is withdrawn from the study because of a treatment-limiting adverse event, thorough efforts should be made to clearly document the outcome.

The Investigator should ensure the accuracy, completeness and timeliness of the data reported to the Sponsor in the CRFs and in all required reports.

15.5 Study Monitoring

It is understood that the responsible Sponsor study monitor (or designee) will contact and visit the Investigator regularly and will be allowed, on request, to inspect the various records of the study (CRFs and other pertinent data) provided that participant confidentiality is maintained in accordance with local requirements.

It will be the monitor's responsibility to inspect the EDC CRFs at regular intervals throughout the study, to verify the adherence to the protocol and the completeness, consistency and accuracy of the data being entered on them. The monitor must verify that the participant received the assigned dose. The monitor should have access to laboratory test reports and other participant records needed to verify the entries in the EDC CRF. The Investigator (or deputy) agrees to cooperate with the monitor to ensure that any problems detected in the course of these monitoring visits are resolved.

15.6 Confidentiality of Clinical Trial Documents and Participants' Medical Records

The Investigator must assure that participants' anonymity will be maintained and that their identities are protected from unauthorized parties. In the EDC CRF or other documents submitted to the Sponsor, participants should not be identified by their names, but by an identification code.

The Sponsor already maintains rigorous confidentiality standards for clinical studies by "coding" (i.e. assigning a unique participant identification (ID) number at the Investigator site) all participants enrolled in Sponsor clinical studies. This means that participant names are not included in data sets that are transmitted to any Sponsor location.

15.7 Clinical Study Report

A Clinical Study Report will be written and submitted to relevant IRB/HREC/EC and regulatory authorities in accordance with local requirements.

15.8 Publication of Data and Protection of Trade Secrets

It is anticipated that the results of this study may be published or presented at scientific meetings. Investigators cannot publish without prior written permission of the Sponsor. Authors must allow a reasonable period for manuscript review of at least 30 days. The Sponsor may delay publication for commercial reasons for up to 6 months.

16 STUDY ADMINISTRATIVE PROCEDURES

This section provides additional information on study-related administrative procedures, definitions, requirements, and record-keeping activities related to the study assessments described in [Section 8](#).

16.1 Subject Recruitment Procedures

Participants will be identified for potential recruitment by the Investigator using recruitment plan agreed upon with Principia, possibly including, but not limited to, a listing from study center, volunteer database, newspaper/radio/internet advertisement, or mailing list.

16.2 Subject Enrollment Procedures

Participants cannot commence enrollment procedures until all entry criteria have been fulfilled. Where the clinical significance of an abnormal screening test result (lab or any other tests) is considered uncertain, the test may be repeated.

The Investigator or designee will enter data for each enrolled participant in the study CRF and enter the corresponding number for allocation to the treatment groups in the appropriate place on each participant's CRF. A participant enrollment and Identification Code List must be maintained by the Investigator or Pharmacist, or designee.

Under no circumstances will participants who enroll in this study and complete treatment as specified be permitted to re-enroll in the study.

16.3 Patient Premature Withdrawal – Definition

A patient who withdraws from the study before taking one or more doses of study drug is considered to have withdrawn from the study early.

16.4 Procedures for Patients Who Withdraw from the Study

Participants have the right to withdraw from the study at any time for any reason. In the event that a participant decides to discontinue from the study, he/she should be asked if he/she can still be contacted for further information. The outcome of that discussion should be documented in both the medical records and in the CRF.

When applicable, participants should be informed of circumstances under which their participation may be terminated by the Investigator without the participant's consent. The Investigator may withdraw participants from the study in the event of intercurrent illness, AEs, treatment failure after a prescribed procedure, lack of compliance with the study and/or study procedures or any other reasons where the Investigator feels it is in the best interest of the participant to be terminated from the study.

Reasons for withdrawal must be documented and explained to the participant. It is understood by all concerned that an excessive rate of withdrawals can render the study uninterpretable; therefore, unnecessary withdrawal of participants should be avoided. Should a participant decide to withdraw, all efforts should be made to complete and report the observations as thoroughly as possible, particularly the follow-up examinations.

The Investigator should contact the participant or a responsible relative either by telephone (followed by registered mail) or through a personal visit to determine as completely as possible the reason for the withdrawal. A complete final evaluation at the time of the participant's withdrawal should be made, with an explanation of why the participant is withdrawing from the study. If the reason for removal of a participant from the study is an AE, the principal specific event must be recorded on the CRF. The participant should be followed until the AE is resolved, if possible.

16.5 Treatment Compliance

Accountability and participant compliance will be assessed by maintaining adequate study drug dispensing records and medication counts. The Investigator is responsible for ensuring that dosing is administered in compliance with the protocol. See [Section 10.4](#) for instructions on Drug Accountability procedures.

16.6 Recording of AEs on the CRF

All AEs encountered during the clinical study will be reported in detail in the source documents and documented in the CRF, from the date of participant consent throughout the follow-up visit. SAEs for which the relationship to test drug is considered "related", should be followed up until they have returned to the baseline status or stabilized. If the cause of the AE is established, it should be described in detail, including supporting information, in the source documents and on the CRF.

16.7 Physical Examination Procedures

At screening and follow-up visits, a complete physical examination will consist of checking the normality or abnormality of the following body systems: general appearance, skin, eyes, ears, nose, throat, heart, chest/breast, abdomen, neurological system, lymph nodes, spine and extremities (skeletal).

An abbreviated physical examination will consist of checking the normality or abnormality of the following body systems: general appearance, abdomen, and cardiorespiratory examination.

The results of the physical examination will be summarized as normal/abnormal. In case of abnormality, details will be recorded in the participant notes and in the CRF.

Height will be recorded at screening only.

16.8 Vital Signs Procedures

Blood pressure (BP), pulse rate, body temperature and respiratory rate will be recorded at the time points specified in the Schedule of Assessments ([Appendix 4](#)).

16.9 Body Weight

Body weight should be measured on the same digital clinic scale, after checking for accurate zero calibration each time. Weight is recorded in kg to one decimal place.

16.10 ECG Procedures

Single 12-lead ECG assessments will be obtained as specified in the Schedule of Assessments ([Appendix 4](#)) to confirm eligibility and to ensure real time safety evaluation of the participants in the study, as specified in the Schedule of Assessments. Unscheduled ECGs may be performed as clinically indicated and recorded in the eCRF.

Participants should be in a resting position for at least 10 minutes prior to any measurement. Body position should also be consistently maintained for each ECG evaluation. In particular, changes in heart rate should be avoided. There should be no environmental distractions (TV, radio, conversation) during the pre-ECG rest and the ECG recording time.

Heart rate (HR), QRS duration and respiratory rate (RR), and QT intervals will be recorded. Changes of the T-wave and U-wave morphology and overall ECG interpretation will be documented.

All ECG recordings must be performed using a standard high-quality, high-fidelity digital electrocardiograph machine equipped with computer-based interval measurements.

For safety monitoring purposes, the Investigator must review, sign and date all ECG tracings. Paper copies will be kept at the study center with the participant's clinical file as part of the permanent record. The ECG intervals and interpretation will be recorded on the CRF.

16.11 Laboratory Test Procedures

The laboratory assessments will be performed at a central laboratory, with the provision for occasional local laboratory testing, if required. Laboratory safety tests shall be collected at time points specified in the Schedule of Assessments ([Appendix 4](#)).

Additional blood or urine samples may be taken at the discretion of the Investigator if the results of any test fall outside the reference ranges, or clinical symptoms necessitate additional testing to monitor participant safety. Where the clinical significance of abnormal lab results is considered uncertain, screening lab tests may be repeated before randomization to confirm eligibility. In the event of unexplained abnormal clinically significant laboratory test values, the tests should be repeated immediately and followed up until they have returned to the normal range, are considered to be clinically stable, and/or an adequate explanation of the abnormality is found.

16.11.1 Recording of Laboratory Test Results on the CRF

Results of clinical laboratory testing will be recorded on the CRF or be received as electronically produced laboratory reports submitted directly from the local or central laboratory, if applicable.

The procedures for the collection, handling and shipping of laboratory samples will be specified in the Sample Collection, Handling and Logistics Manual.

16.12 Recording of Concomitant Medications on the CRF

All medications (prescription and over-the-counter [OTC]) taken within 28 days prior to study screening (reference [Exclusion Criteria, Item #5](#)) will be recorded in the CRF.

APPENDIX 1A CORTICOSTEROID RESCUE CRITERIA AND TREATMENT PROTOCOL (PART A)

Systemic corticosteroids will be avoided during PRN1008 monotherapy unless these rescue criteria are triggered, as described below, or if patients enter the study on low doses (≤ 0.5 mg/kg mg per day). In each rescue scenario, the recommended method of corticosteroid taper is shown in [Appendix 7](#).

Rescue Criteria #1: Flare which, in the mind of investigator, is potentially life threatening

- Commence conventional immunosuppressive therapy and discontinue PRN1008

Rescue Criteria #2: Development of severe but not life-threatening PV (defined as PDAI score ≥ 45) at any time during PRN1008 therapy:

- If most recent BTK trough occupancy was 50% or more, commence conventional immunosuppressive therapy and discontinue PRN1008
- If most recent BTK trough occupancy was $< 50\%$ and PRN1008 dose has not been increased since last BTK assay, commence, or increase dose to, full-dose prednis(ol)one (1.0 mg/kg) orally and increase dose of PRN1008 by an amount agreed to with the Sponsor's Medical Monitor. At next review:
 - If not responding, commence conventional immunosuppressive therapy and discontinue PRN1008
 - If responding, maintain or taper corticosteroids as clinically appropriate while maintaining PRN1008 treatment
- If no BTK trough occupancy is available to guide therapy, maintain PRN1008, and commence, or increase to, full-dose prednis(ol)one (1.0 mg/kg) orally. Seek to expedite latest BTK trough occupancy test result or arrange for a new blood draw to measure BTK trough occupancy. At next review:
 - If not responding, commence conventional immunosuppressive therapy and discontinue PRN1008
 - If responding, maintain or taper corticosteroids as clinically appropriate while maintaining PRN1008 treatment (including adjust dose upwards if BTK trough occupancy $< 50\%$ in consultation with the Sponsor Medical Monitor)

Rescue Criteria #3: Patients with non-severe PV but who fail to achieve “Control of Disease Activity (CDA*)” by 4 weeks

- If most recent BTK trough occupancy was 50% or more, commence, or increase dose to, low dose prednis(ol)one (0.5 mg/kg) orally. Review after another ~2 weeks:
 - If not responding, commence conventional immunosuppressive therapy and discontinue PRN1008
 - If responding, maintain or taper corticosteroids as clinically appropriate while maintaining PRN1008 treatment
- If most recent BTK trough occupancy was < 50% and PRN1008 dose has not been increased since last BTK assay, increase dose of PRN1008 by an amount agreed to with the Sponsor’s Medical Monitor. At review after another ~2 weeks:
 - If not responding, commence, or increase dose to, low-dose prednis(ol)one (0.5 mg/kg) orally and maintain PRN1008 treatment. If a dose of ≥ 0.5 mg/kg is already in use, or if after further review the patient is still not responding, commence conventional immunosuppressive therapy and discontinue PRN1008.
 - If responding, maintain PRN1008 treatment and consider tapering of prednis(ol)one

In each rescue scenario, the recommended method of corticosteroid taper is shown in [Appendix 7](#).

When patients enter the study on corticosteroids, the dose should be maintained for the initial 2 weeks of PRN1008 therapy if possible in order to evaluate the additive effects of PRN1008. During this time and subsequently, the rescue criteria should be followed if indicated. In other words, in some circumstances the corticosteroid dose should be increased, with or without cessation of PRN1008. If patients respond well to PRN1008 without increasing the corticosteroid dose, the Werth taper ([Appendix 7](#)) should be commenced after four weeks of PRN1008 therapy.

*As defined by the EADV 2014 Pemphigus S2 Guideline ([Hertl et al. 2015](#))

APPENDIX 1B CORTICOSTEROID RESCUE CRITERIA AND TREATMENT PROTOCOL (PART B)

Systemic corticosteroids will be avoided during PRN1008 monotherapy unless these rescue criteria are triggered, as described below, or if patients enter the study on low doses (≤ 0.5 mg/kg mg per day). In each rescue scenario, the recommended method of corticosteroid taper is shown in [Appendix 7](#).

Rescue Criteria #1: Flare which, in the mind of investigator, is potentially life threatening

- Commence conventional immunosuppressive therapy and discontinue PRN1008

Rescue Criteria #2: Development of severe (defined as PDAI score ≥ 45) but not life-threatening PV or clinically significant worsening of already severe PV during PRN1008 therapy:

- Commence, or increase dose to, full-dose prednis(ol)one (1.0 mg/kg) orally and increase dose of PRN1008 by an amount agreed to with the Sponsor's Medical Monitor to a maximum of 600 mg bid. At next review:
 - If not responding, commence conventional immunosuppressive therapy and discontinue PRN1008
 - If responding, maintain or taper corticosteroids as clinically appropriate while maintaining PRN1008 treatment.

Rescue Criteria #3: Patients with non-severe PV but who fail to achieve "Control of Disease Activity (CDA*)" by 4 weeks

- If partially responding, increase dose of PRN1008 if not already maximal (Table 4), review in 1-2 weeks, and then consider additional CS up to a dose of 0.5 mg/kg. If subsequently responding, maintain PRN1008 treatment and taper prednis(ol)one.
- If not responding, increase dose of PRN1008 if not already maximal (Table 4), review in 1-2 weeks, and then consider additional CS up to a dose of 1.0 mg/kg. If subsequently responding, maintain PRN1008 treatment and taper prednis(ol)one.

Table 4 Dose Escalation Rules Part B

Current Dose	Inadequate Clinical Response ¹ Dose-Escalation Rules
400 mg qd	Increase to 400 mg bid (allowed at Week 3 visit or later) ²
400 mg bid	Increase to 600 mg bid (allowed at Week 5 visit or later) ²
600 mg bid	No dose increase possible.

1. Investigator discretion: Generally, clinical response is shown by some improvement seen in first 2 weeks with CDA achieved by the Week 5 visit
2. Unless tolerability issues preclude dose-escalation

In each rescue scenario, the recommended method of corticosteroid taper is shown in [Appendix 7](#).

When patients enter the study on corticosteroids, the dose should be maintained for the initial 2 weeks of PRN1008 therapy if possible in order to evaluate the additive effects of PRN1008. During this time and subsequently, the rescue criteria should be followed if indicated. In other words, in some circumstances the corticosteroid dose should be increased, with or without cessation of PRN1008. If patients respond well to PRN1008 without increasing the corticosteroid dose, the Werth taper ([Appendix 7](#)) should be commenced after four weeks of PRN1008 therapy.

* As defined by the EADV 2014 Pemphigus S2 Guideline ([Hertl et al. 2015](#))

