
Participant Selection Criteria:
	
Inclusion Criteria Part A and Part B (unless noted below):
 
 1. Male or female patients, aged 18 to 80 years old, with biopsy-proven (positive direct immunofluorescence and appearance on H&E microscopy), mild-moderate PV in Part A (PDAI 8 to 45) and mild-severe PV in Part B (PDAI 8 to 60) 2. Newly diagnosed or relapsing patients for whom an initial period of PRN1008 monotherapy or combination therapy with low-dose corticosteroids (≤ 0.5 mg/kg of prednis[ol]one or equivalent), is judged clinically acceptable, provided tapering of the corticosteroid treatment regimen is anticipated with good clinical response to PRN1008 3. BMI > 17.5 and < 40 kg/m² Part A only 4. Adequate hematologic, hepatic, and renal function (absolute neutrophil count $\geq 1.5 \times 10^9/L$, Hgb > 9 g/dL, platelet count $\geq 100 \times 10^9/L$, AST/ALT $\leq 1.5 \times$ ULN, albumin ≥ 3 g/dL, creatinine \leq ULN (Part A) and creatinine $\leq 1.5 \times$ ULN (Part B)) 5. Female patients who are of reproductive potential must agree for the duration of active treatment in the study to use an effective means of contraception (hormonal contraception methods that inhibits ovulation, intrauterine device, intrauterine hormone-releasing system, bilateral tubal ligation, vasectomized partner, condoms or sexual abstinence). Unless surgically sterile, postmenopausal females should have menopause confirmed by FSH testing 6. Able to provide written informed consent and agreeable to the schedule of assessments 
Exclusion Criteria Part A and Part B:
 
 1. Previous use of a BTK inhibitor. 
Patients enrolled in a previous version of this protocol who are still in their 12-week active treatment period with PRN1008 are eligible to continue treatment, initially with their current dose level, under this amended protocol for an additional 12 weeks, i.e.

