2 RATIONALE AND JUSTIFICATION FOR THE STUDY AND THE STUDY DESIGN

2.1 Rationale for the Study Design

This open-label, pilot study is designed to explore the initial efficacy and safety of PRN1008 in PV and to enable the accurate design of pivotal randomized clinical trials which are to follow. An open-label design was chosen for several reasons: PV does not spontaneously remit so there is no placebo effect to account for; clinicians need to know when to use rescue corticosteroids, if necessary, in a timely manner; and lastly, the pilot nature of the investigation itself is best explored in an open-label fashion.

Because of the ability to guide individualized dosing with BTK occupancy measurement, the use of which has been validated in a naturally occurring canine pemphigus study, this assay was used to supplement the clinical response assessments in making dose-adjustments in **Part A**. More than 95% of patients in **Part A** (20/21) had adequate BTK occupancies (mean 86% pre dose at steady-state). In **Part B**, the clinical efficacy of the 400 mg qd dose is being explored to see if lower BTK occupancies will still equate to clinical efficacy. For this reason, clinical response alone, and not BTK occupancies, is recommended to guide dose adjustment in **Part B**.

Given the efficacy seen in this pemphigus study to date at varied clinical severities, and the updated, supporting, chronic, GLP toxicology ([Section 1.3](#)), there is clinical equipoise to study PRN1008 monotherapy (or with low dose CS) in patients with mild-to-severe (baseline PDAI 8-60), corticosteroid-naïve or relapsing PV, with close observation and appropriate corticosteroid rescue protocols.

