400 mg bid	Increase to 600 mg bid (allowed at Week 5 visit or later)**
600 mg bid	No dose increase possible. See Appendix 1B for corticosteroid rescue protocol

[figure not shown]
* Investigator discretion: Generally, clinical response is shown by some improvement seen in first 2 weeks with CDA achieved by the Week 5 visit

** Unless tolerability issues preclude dose-escalation

[figure not shown]

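### Part B admits patients up to PDAI 60, but Appendix 1B has no rescue criterion for one who enters severe, does not worsen and has no CDA at 4 weeks

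*Protocol*

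**What the plan says.** Entry limits differ by part. Inclusion Criterion 1 (Synopsis and Section 6.1) admits "mild-moderate PV in Part A (PDAI 8 to 45) and mild-severe PV in Part B (PDAI 8 to 60"). Section 2.1 supports the wider Part B range on the footing that patients are treated "with close observation and appropriate corticosteroid rescue protocols".

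Appendix 1B opens with the rule that "Systemic corticosteroids will be avoided during PRN1008 monotherapy unless these rescue criteria are triggered", apart from patients who enter on low doses. It then gives three criteria:

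- **#1** needs a flare that the investigator judges potentially life-threatening.
- **#2** needs either the development of severe PV, defined as PDAI 45 or more, or "clinically significant worsening of already severe PV during PRN1008 therapy".
- **#3** is the non-response criterion at 4 weeks. It begins "Rescue Criteria #3: Patients with non-severe PV but who fail to achieve" CDA.

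Section 6.3.2 makes immunosuppressants other than low-dose corticosteroids depend on a triggered rescue criterion. Table 3 (Section 4.6) allows PRN1008 escalation for inadequate response without regard to severity. Its 600 mg bid row reads "No dose increase possible. See Appendix 1B for corticosteroid rescue protocol".

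**The concern.** Criterion #2 was extended for Part B to cover patients who are severe at entry. Appendix 1A has only "Development of severe but not life-threatening PV (defined as PDAI score" of 45 or more), and Appendix 1B adds worsening of existing severe disease. The population named in criterion #3 was left as it stands in Part A. The two edits do not meet, and severe patients who are static fall between them.

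Two things are at stake. The first is protection: the stated rules give a milder non-responder a named route at 4 weeks and a sicker one none, although Section 2.1 relies on the rescue rules to justify enrolling the sicker one. The second is interpretation. If steroids are added for such a patient without a criterion to follow, that use enters three summaries in the Part B SAP: cumulative steroid dose (5.4.2.3), steroid dose by visit (5.4.2.4) and CR split at 0.5 mg/kg (5.4.2.1). The SAP's listing of rescue medication carries a rescue-criterion column, and none of the three criteria would describe this use.

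**Working it through.** The plan gives no figure to reproduce here. The check is whether the three criteria cover the population that Part B admits.

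**Inputs.** Part B entry range PDAI 8 to 60 (Section 6.1). Severe means PDAI 45 or more (Appendix 1B, criterion #2). Criteria #1 to #3 as above. Both patients below have no CDA at the Week 5 visit and no life-threatening flare.

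| Criterion | Enters at 44, still 44 | Enters at 52, now 50 |
|---|---|---|
| #1 life-threatening flare | not met | not met |
| #2 severe disease newly developed, or existing severe disease worse | not met | not met |
| #3 non-severe and no CDA by 4 weeks | **met** | not met |

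**All entry scores.** Let b be the baseline and p the Week 4 PDAI, with p no higher than b.

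- Criterion #2 is met if (b < 45 and p ≥ 45) or (b ≥ 45 and p > b).
- Criterion #3 is met if p < 45 and there is no CDA.

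Running every whole-number b from 8 to 60 and every p from 0 to b gives:

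- For b = 8 to 44, p is always below 45, so criterion #3 always applies and no state is uncovered.
- For b = 45 to 60, every p from 45 to b is uncovered. That is 60 − 45 + 1 = 16 of the 60 − 8 + 1 = 53 admissible scores.

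Counting any rise as worsening is generous to the plan, because criterion #2 asks for clinically significant worsening. A severe entrant who falls below 45 without CDA comes under criterion #3 and is not part of the gap.

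**When the Table 3 cross-reference fails.** A newly enrolled Part B patient starts at 400 mg qd, may move to 400 mg bid from the Week 3 visit and to 600 mg bid from the Week 5 visit. Failure at 600 mg bid can therefore be seen only after the Week 5 visit. The next scheduled visit is Week 9 (Appendix 4).

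**Which results are exposed.** The Part B primary endpoint is CDA on or before the Week 5 visit (Part B SAP 5.4.1). The gap opens at that visit, so the endpoint has largely been decided by then. Part B plans no hypothesis testing (SAP 3.8). What can move is descriptive and later.

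**The case against.** The strongest reply is that these patients are not stranded, and much of it stands.

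- **Escalation is open at any severity.** Under criterion #3 the first step for the milder patient is also a PRN1008 increase with review in 1 to 2 weeks. Added steroid is only something to consider afterwards. The severe patient can be escalated too, under Table 3. What that patient lacks is the named short review and the steroid step.
- **Judgment is built in.** Section 4.6 asks investigators to weigh benefit and risk, and its stopping advice is general guidance. Section 16.4 allows withdrawal for treatment failure. The Synopsis labels the rescue criteria as guidelines.
- **Low-dose steroid is not clearly barred.** Section 6.3.2 exempts it from the immunosuppressant restriction, and Appendix 1B says steroids are to be avoided, which is weaker than a prohibition.

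Four stronger readings are tempting, and the documents do not support them. A reader might infer that withdrawal is the only backstop; escalation and investigator judgment show otherwise. A reader might infer that the patient goes some 20 weeks without recourse. That starts the clock before 600 mg bid can have failed, and assumes no worsening, response or withdrawal for the rest of treatment. A reader might turn 16 of 53 scores into about 30% of patients, but that is a count of scores and says nothing about frequency. Finally, a reader might infer that a Part A patient entering at PDAI 45 would be rescued for baseline disease and scored a primary non-responder. That treats disease present at entry as having developed on treatment, the opposite of the reading on which the Part B gap rests.

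None of this supplies a criterion. Section 4.6's stopping advice needs poor tolerability as well as poor response. Withdrawal ends participation and is not rescue on study. Steroid above the low-dose allowance, and other immunosuppressants, remain tied to a trigger that this patient cannot meet.

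**Conclusion.** The gap is real and narrow. It covers Part B patients with entry PDAI 45 to 60 who are still at 45 or more, have no clinically significant worsening and have no CDA at 4 weeks. It bites hardest once 600 mg bid has failed, because Table 3 then points to an appendix with no matching criterion.

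The documents do not say how many patients this is. For scale only, at the planned 25 in Part B (Section 11.4) each such patient is 1/25 = 4 percentage points of a Part B proportion. The primary result is largely untouched; the cost falls on patient protection and on the descriptive steroid and CR summaries after Week 5.

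The conclusion assumes that development of severe PV does not include disease already severe at entry. The wording of criterion #2 supports this, since it treats existing severe disease separately and requires worsening.

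A minor note on Part A: PDAI 45 is both the upper limit of the mild-moderate entry range and the threshold for severe in Appendix 1A. The two should be reconciled. The Part B SAP (2.2) also still gives PDAI 8 to 45 for each part, so the wider range was not carried through there either.

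**What to change.** Reconcile Appendix 1B criteria #2 and #3 with the PDAI 8 to 60 inclusion criterion, so that a patient severe at entry, not worse and without CDA at 4 weeks falls under a named criterion. Make the 600 mg bid row of Table 3 lead to that criterion. State how the opening rule of Appendix 1B fits with the low-dose exemption in Section 6.3.2. Which action follows is for the sponsor's clinicians to decide; none is proposed here.

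Align the PDAI range in Part B SAP 2.2 with the protocol, and make the Part A entry limit and the severe threshold consistent at 45. If any patient has already fallen into the gap, identify that patient and the steroids given in the study report.

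The cost is a wording amendment with the usual ethics review, and no added visits or procedures.
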